### 2.3.2 Outcomes for secondary and CCI objectives

[figure not shown]
#### Outcomes to Achieve Secondary Objectives

Secondary objective	Outcome definition	Number of objective
To evaluate the correlation of sensor collected data with 
 
a) patients' self-assessed health status and symptoms (CAT) at baseline and study end,
 
b) lung function and lab values at baseline and study end,
 
c) and with history of mild, moderate and severe exacerbations at study end.
 
	a) Patients' health status and symptoms at baseline (Day 0) and study end will be measured as the summary score across items of the CAT questionnaire that consists of 8-items in which participants can choose a score from 0 to 5, for each visit b) Lung function will be assessed using plethysmography and lab values including Complete Blood Count with differential, Blood Gas Analysis, procalcitonin and CRP will be assessed as per standard practice at baseline (Day 0) and at study end (for details see Section 2.1.3) c) number, date of onset and duration of mild, moderate, and severe exacerbations, respectively, during the observation period	3
Sensor derived data may be related to the CAT score, therefore, an additional objective is to investigate whether changes in physical activity, heart rate, heart rate variability, temperature, respiration rate, cough frequency, and sleep pattern in the 3-month observation period, are associated with changes	Please see above (3a) During the observation period the CAT score will be obtained on a daily basis. Daily summary score across items of the CAT questionnaire will be computed.	4

of the patient self-assessed symptoms (CAT).		
To build a model for predicting patient self-assessed symptoms (CAT) score on daily basis and change in the CAT score (and change of CAT score by 2 points or more considered as MCID) employing sensor collected data on physical activity, heart rate, heart rate variability, temperature, respiration pattern, cough frequency, and/or sleep pattern.	Patients' health status and symptoms at baseline (Day 0) will be measured as the summary score across items of the CAT questionnaire that consists of 8-items in which participants can choose a score from 0 to 5. During the observation period the CAT score will be obtained via a digital application on a daily basis.	5

CCI

CCI

### 2.3.3 Safety outcomes

#### **Adverse Events**

Adverse events are continuously collected in both cohorts throughout the observation period and coded according to current version of WHO MedDRA dictionary.

#### **Adverse device effects (ADE)**

Adverse events possibly, probably, or causally related to the use of a medical device or procedures.

This includes any adverse event resulting from insufficient or inadequate instructions for use, deployment, implantation, installation, operation, or any malfunction of the medical device used in the study. This includes any event that is a result of a use error or intentional misuse.

## 3 DATA ANALYSIS

### 3.1 OVERVIEW OF PLANNED ANALYSES

There will be a single analysis after last-patient-out during the study close-out phase to support the clinical investigation report.

### 3.2 ANALYSIS SETS

The study will have two main analysis sets:

- COPD cohort: all patients with COPD fulfilling all of the inclusion criteria and none of the exclusion criteria (see Section 1.3.1);
- Calibration cohort: participants in the calibration cohort as defined in Section 1.3.1

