9.7.1 Analysis Sets

Two Analysis Sets will be defined:

1. Participants with COPD including all patients with COPD included in the study, i.e, all patients with COPD fulfilling all of the inclusion criteria and none of the exclusion criteria (see Section 9.2.2).
2. Participants in the calibration cohort included in the study (see Section 9.2.2).

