11.4 Recording of Adverse Events

The recording period for (S)AEs/DDs begins when the participant is initially included in the study (date of signature of first informed consent) and continues until the last study protocol-specific procedure.

During the conduct of the study, the Investigator must fully record all the following:

- any AE;
- any SAE;
- any DD that might have led to a serious adverse event if appropriate action had not been taken, intervention had not occurred, or circumstances had been less fortunate;
- any new findings in relation to any event referred to in the previous points.

AEs/DDs must be reported by the participant (or, when appropriate, by a caregiver, surrogate, or the participant's legally authorized representative) to the Investigator during visits defined in the SoA of the study protocol. The Investigator must record all directly observed events and all spontaneously reported events by the study participant. In addition, each study participant will be questioned about AEs/DDs.

All safety data AEs/SAEs, as specified above, occurring during the study, must be documented and recorded in the Case Report Form (CRF) by the Investigator, including its description, seriousness, severity (grading), duration (onset and resolution dates), causal relationship, any other potential causal factors, actions taken with the device, required treatment and outcome of the AE.

Company substance code **INN**
MS202559_0001

All SADEs and DDs must be also documented and recorded in the SADE Report Form and the DD Report Form, respectively, by the Investigator within 24 hours of awareness.

All AEs must be recorded in the participant's medical record and on the AE form in the eCRF. Investigators should use correct medical terminology/concepts when recording AEs on the AE form in the eCRF and avoid colloquialisms and abbreviations. Only 1 AE term should be recorded in the event field on the AE form in the eCRF. All AE terms will be coded with the most recent MedDRA version by the sponsor.

AE without resolution between participant evaluation time points should only be recorded once in the eCRF. In case there is an increase in severity and/or seriousness of the event, a new AE with the new severity and/or seriousness must be recorded as a separate event on the AE form in the eCRF.

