#### 3.4.1 General specifications

Descriptive statistics will be provided for study variables and measurement time points as specified in the following sections. Unless indicated otherwise, descriptive statistics will include the number of observations and missing values, means, standard deviations, medians, interquartile range, Q1, Q3, minimum, and maximum. Results for continuous variables (e.g., age at diagnosis) and correlation coefficients will be reported with at least 3 figures as rounded numbers with 2 decimal values. Descriptive statistics for categorical variables will report n (%), missing and with number (n) equal to the total number of patients at each category level (without missing) during the assessment period and will be reported with 3 figures as percent with 1 decimal value.

Medical history, adverse events and prior/concomitant medication will be summarized using coded preferred terms by proportion of patients with at least one occurrence relative to the number of patients in the cohort.

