#### *3.4.5.10 Analysis of safety outcomes*

##### Adverse device effects

There is a very low likelihood for ADEs to occur in this study. Any such events will be reported in a listing, containing Subject ID, Site ID, Sex, Age, COPD Severity, Reported Term, Preferred Term, System Organ Class, Serious Flag, Severity, Outcome. ADEs are collected in both cohorts.

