#### Adverse events

Adverse events are continuously collected throughout the observation period in both cohorts. A frequency table will describe AE occurrence by severity.

Proportions of AE will be reported by preferred term and system organ class according to WHO MedDRA dictionary (latest version).

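### No analysis set covers every patch recipient, so adverse events in a participant found ineligible after hand-out are recorded but, read literally, left out of the AE tables

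*SAP*

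**What the plan says.** SAP 3.2 states "The study will have two main analysis sets" and lists them. The first is "COPD cohort: all patients with COPD fulfilling all of the inclusion criteria and none of the exclusion criteria". The second is "Calibration cohort: participants in the calibration cohort as defined in Section 1.3.1", and Section 1.3.1 is where the SAP sets out eligibility. Protocol 9.7.1 also has two sets. The first reads "Participants with COPD including all patients with COPD included in the study, i.e, all patients with COPD fulfilling all of the inclusion criteria", and the same sentence goes on to require that no exclusion criterion is met. The second is the calibration participants included in the study.

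On safety, SAP 3.4.1 summarises adverse events, along with medical history and medication, "by proportion of patients with at least one occurrence relative to the number of patients in the cohort". The AE paragraph of SAP 3.4.5.10 reads "Adverse events are continuously collected throughout the observation period in both cohorts. A frequency table will describe AE occurrence by severity", and it adds proportions by preferred term and system organ class. The paragraph on adverse device effects (ADEs) plans a subject-level listing of any that occur and notes that "ADEs are collected in both cohorts".

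Under protocol 11.4 the recording period "begins when the participant is initially included in the study (date of signature of first informed consent" and runs to the last study-specific procedure. It carries no eligibility condition.

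**The concern.** Safety results are normally tabulated on everyone exposed, whether or not they turn out to meet the entry criteria. Here the only sets defined are built from eligibility, and the AE summaries take the cohort as denominator. A programmer who follows the text would drop an ineligible wearer from both numerator and denominator, although the events are in the database.

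Two features of the plan make this more than a formality. First, some exclusion criteria (implanted electronic devices, known sensitivity to silicon or hydrogel) plausibly bear on how the patch is tolerated, so a violator may be informative about safety. Second, the device carries a temperature function that the Notified Body has not evaluated (protocol 9.1.1), and this single analysis supports the clinical investigation report (SAP 3.1). The AE tables in that report should describe all wearers.

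**Working it through.** **1. Following one participant through the text.** Take a COPD participant who receives the patch and is later found to have broken a criterion.

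| Step | Place | Outcome on a literal reading |
|---|---|---|
| Patch handed out | Protocol 9.2.2 | Meant for eligible participants only, so the case arises when ineligibility is found afterwards |
| Stays in the study? | Protocol 9.2.5 | Late-found ineligibility is not a listed withdrawal reason, so wear may continue for up to 3 months |
| AEs recorded? | Protocol 11.4 | Yes, from consent |
| In an analysis set? | SAP 3.2, protocol 9.7.1 | No |
| In the AE proportions? | SAP 3.4.1, 3.4.5.10 | No, because the cohort is the denominator |
| In the ADE listing? | SAP 3.4.5.10 | Yes on its wording: no eligibility filter and no denominator |
| In serious device effect and device deficiency reporting? | Protocol 11.5, 11.6 | Yes: does not depend on analysis sets |
| Visible in disposition? | SAP 3.4.9 | Eligibility violations appear as screening failures; the listed early-discontinuation reasons do not cover this case |

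The loss is therefore confined to the AE frequency tables and proportions.

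**2. Who counts as eligible is itself unclear.** Protocol 9.2.1, COPD inclusion criterion 4, requires at least one moderate or severe exacerbation in the last 12 months. SAP 1.3.1 omits that part, although the study-size text in SAP 1.3.2 assumes at least one exacerbation in that period. The same wearer can be inside the set by SAP 1.3.1 and outside it by the protocol.

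**3. The plan's own figure.** SAP 1.3.2 and protocol 9.5 need 60 participants and allow 10% drop-out: 60 / (1 − 0.10) = 66.7, rounded up to 67. This reproduces the stated 67. It is used below only as a denominator.

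**4. Illustration under assumptions.** The documents give no rate of ineligibility found after hand-out and no expected AE rate. Let k of 67 be found ineligible, and let each participant have an AE with probability r.

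- Share of COPD wearers missing from the tables, k/67: 1/67 = 1.5%, 3/67 = 4.5%, 5/67 = 7.5%.
- Chance that at least one participant with an AE is lost, 1 − (1 − r)^k, for r from 0.10 to 0.50:
  - k = 1: 10% to 50%
  - k = 3: 1 − 0.9³ = 27% to 1 − 0.5³ = 88%
  - k = 5: 1 − 0.9⁵ = 41% to 1 − 0.5⁵ = 97%

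**5. Direction.** Let x of the 67 have an AE, y of them among the k ineligible. The full proportion is x/67 and the tabulated one is (x − y)/(67 − k). The tabulated figure is lower only if y/k exceeds x/67. With r = 0.30, x is about 0.30 × 67 = 20, and 20/67 = 29.9%.

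- k = 3: from 17/64 = 26.6% (y = 3) to 20/64 = 31.3% (y = 0)
- k = 5: from 15/62 = 24.2% (y = 5) to 20/62 = 32.3% (y = 0)

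The tabulated proportion can move either way.

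**The case against.** The strongest reply is that the plan never says anyone is removed after enrolment. Protocol 9.2.2 fixes the COPD cohort as patients eligible at Day 0, protocol 9.7.1 treats included and eligible as the same group, and late-found ineligibility is not a withdrawal reason. The set could then be everyone enrolled as eligible at Day 0. This reading is possible, but SAP 3.2 does not state it and its literal wording points the other way.

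SAP 3.2 calls its two sets the main ones, and table populations could be given in the TLF plan of Appendix 1, whose content is not visible in the public document. That stands as a limit on what can be checked. Even so, no other set is defined in the SAP text itself. The safety section also does not cite SAP 3.2, so the link rests on the word cohort and on SAP 3.4.1.

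The examples have limits too. Only known sensitivity is an exclusion, so a first skin reaction breaks no criterion. Arrhythmia excludes only where the investigator judges that it would interfere.

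Safety is not a stated objective, and the protocol says it does not aim to evaluate the device. This lowers the priority, but the AE tables are still planned and still need a population.

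A reader might go further and infer that an observed device effect could be reported as zero. The documents do not support that: ADEs go into a listing with no filter and no planned proportion, and serious device effects and deficiencies are reported whatever the analysis set. Nor do they support saying that both cohorts are explicitly restricted. For calibration the SAP restriction is only by cross-reference, and protocol 9.7.1 refers simply to those included.

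**Conclusion.** The point holds in a limited form. On a literal reading of SAP 3.2 and 3.4.1, adverse events of a COPD participant found ineligible after receiving the patch are recorded but left out of the AE frequency tables and proportions. The same applies to calibration participants if the cross-reference to Section 1.3.1 is read as requiring eligibility. AE recording, the ADE listing and expedited or quarterly device reporting are not affected on their wording.

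The size is unknown. The figure of 1.5% to 7.5% of COPD wearers rests on an assumed 1 to 5 violators among 67. The direction is unknown as well. It is tempting to infer that AE proportions are biased downward because violators are at higher risk, but nothing in the documents shows that they are. The conclusion assumes that the cohort in SAP 3.4.1 is the set in SAP 3.2, that eligibility is not frozen at Day 0, and that the unseen TLF plan does not already name an all-recipient population.

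**What to change.** Add a third set to SAP 3.2 and protocol 9.7.1: a safety set of all participants in either cohort who received a patch, regardless of eligibility, shown by cohort. Then:

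- use it as population and denominator for the AE tables in SAP 3.4.5.10 and the AE summaries in SAP 3.4.1;
- state that the ADE listing covers the same set;
- list AEs that occur between consent and hand-out separately;
- leave the two existing sets unchanged for the objectives.

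The 12-month element of COPD inclusion criterion 4 must also be reconciled between protocol 9.2.1 and SAP 1.3.1, so that membership of the existing COPD set is unambiguous.

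The cost is one definition in each document and a changed population label on the AE tables. All the data are already collected and no sample-size figure changes. The denominator of the AE tables may differ slightly from that of the objective analyses, and a footnote can say so. If the TLF plan already specifies such a population, the change amounts to stating it in SAP 3.2.

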### 3.3 AMENDMENTS TO THE STATISTICAL ANALYSIS PLAN

Not applicable.

### 3.4 STATISTICAL ANALYSIS

Standard analyses and descriptive statistics will be carried out using R 4.2 or higher (The R Foundation for Statistical Computing, Vienna, Austria). Linear and mixed models will be fit using SAS 9.4 or higher (SAS Institute Inc., Cary, NC, USA) or using R 4.2 or higher (The R Foundation for Statistical Computing, Vienna, Austria). Machine learning models will be implemented using Python 3.8 or higher (The Python Software Foundation, Wilmington, Delaware, USA).

The creation of tables, listings and figures will follow the descriptions provided in Appendix 1) TLF plan.

#### 3.4.1 General specifications

Descriptive statistics will be provided for study variables and measurement time points as specified in the following sections. Unless indicated otherwise, descriptive statistics will include the number of observations and missing values, means, standard deviations, medians, interquartile range, Q1, Q3, minimum, and maximum. Results for continuous variables (e.g., age at diagnosis) and correlation coefficients will be reported with at least 3 figures as rounded numbers with 2 decimal values. Descriptive statistics for categorical variables will report n (%), missing and with number (n) equal to the total number of patients at each category level (without missing) during the assessment period and will be reported with 3 figures as percent with 1 decimal value.

Medical history, adverse events and prior/concomitant medication will be summarized using coded preferred terms by proportion of patients with at least one occurrence relative to the number of patients in the cohort.

#### 3.4.2 Considerations for potential confounders and effect modifiers

Not applicable. All available features will be considered in the predictive modelling.

For objective 4, smoking status, and other relevant baseline covariates will be forced into the models.

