8.1 Primary Objectives

1. To describe the distribution of sensor collected data on physical activity, heart rate, heart rate variability, temperature, respiration rate, cough frequency, and sleep pattern, by severity of COPD exacerbations.
2. To predict moderate or severe COPD exacerbations by building a statistical model employing sensor-derived data and demographic and medical covariates.

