2	To predict moderate or severe COPD exacerbations by building a statistical model employing sensor-derived data and demographic and medical covariates.	Severe/moderate COPD exacerbations (requiring a physician's intervention, emergency room visit or hospitalization) during the observation period.	
COPD exacerbation from the physician charts (for the severe/moderate exacerbation):
 
 - Occurrence (Yes/No) of COPD exacerbation - Severity of COPD exacerbation (moderate, severe) 
Sensor data (Vivalink wearable device) collected daily:
 
 - Physical activity including stair climbing (derived parameter) - Heart rate as beats per minute [daily average] (derived parameter) - Resting heart rate [daily average] (derived parameter) - Heart rate variability [daily average] (derived parameter) - Temperature [daily average, minimum -maximum values] - Respiration rate (breath per minute) [daily average] (derived parameter) - Ratio of in- vs expiration time [daily average min-max] (derived parameter) - Cough frequency (derived parameter) - Sleep pattern (derived parameter) 
Self-reported activities (e.g., coughing, sports, sleeping) as collected by the participant app:
 
 - Coughing - coughing with sputum production - spray use, non-scheduled spray use - eating, going to bed, waking up - walking, climbing stairs - physical exercise 
Other covariates (at Day 0) from the physician chart:
 
 - Demographics data at baseline: (sex, age, height, and weight, race and ethnicity) - Body mass index will be calculated based on height and weight - Smoking status (current, ex-, non-smoker) - Medical history at baseline - Date of diagnosis of COPD

Number of objective	Objective	Outcome definition	Variables and Sources

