#### 2.1.4 Sensor measurements by Vivalink wearable device and ePRO diary

Unless indicated otherwise, the following variables are measured continuously throughout the observation period.

- Physical activity including stair climbing, (calculated based on continuous accelerometer measurement) [daily average] (derived parameter)

- Heart rate as beats per minute [daily average]
- Resting heart rate (resting state as determined by accelerometer, beats per minute) [daily average] (derived parameter)
- Heart rate variability reflecting differences in time intervals between 2 R-waves in the ECG (milliseconds) [daily average] of the following parameters:
  - SDRR (standard deviation of RR intervals),
  - SDNN (standard deviation of NN intervals),
  - SDNNI (Mean of the standard deviations of all the NN intervals for each 5 min segment of a 24 h HRV recording),
  - RMSSD (Root Mean Sum of Squared Distance),
  - ln(RMSSD) (natural logarithm of RMSSD),
  - pNN50 (percentage of successive RR intervals that differ by more than 50 ms)
  - SI (stress index),
  - LF power (low frequency fraction of HRV, 0.04 – 0.15 Hz),
  - HF power (high frequency portion of HRV, 0.15 – 0.40 Hz),
  - LF/HF (ratio of LF-to-HF power) (derived parameter)
- Temperature [daily average, minimum and maximum values] (derived parameter)
- Respiration rate (breath per minute) [daily average, minimum and maximum values]
- Ratio of in- vs expiration time [daily average, minimum and maximum values] (derived parameter)
- Cough frequency (derived parameter, count per day)
- Sleep pattern (derived parameter, hours of sleep)
- Self-reported activities as collected by the participant app, logged as activity per time-stamp, allowing for several logs of the same activity per day:
  - coughing,
  - coughing with sputum production,
  - spray use,
  - non-scheduled spray use,
  - eating,
  - going to bed,
  - waking up,
  - walking,
  - climbing stairs,
  - and physical exercise

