## 2.3 OUTCOME DEFINITIONS

### 2.3.1 Outcomes for primary objectives

The primary outcomes are based on COPD exacerbations. Exacerbations are classified as

- 1) mild if they are treated with short-acting bronchodilators only,
- 2) moderate if they are treated additionally with antibiotics or oral corticosteroids, or
- 3) severe if the patient visits the emergency room or requires hospitalization because of an exacerbation.

The occurrence of exacerbations during the observation period is measured as follows.:

- For moderate/severe exacerbation requiring a physician's intervention, exacerbation details will be recorded via eCRF by the clinical site. Severity, onset and duration will be derived according to the definition above from the documented COPD medication associated with the patients' exacerbation visit. The definition details for COPD medication and ATC codes will be finalized during the planned Data review meeting prior to the final analysis.
- For mild exacerbations: self-reported; treated by the participant without intervention by a physician will be documented in the patient application labeling section (days with added treatment: short-acting bronchodilators only). The start date and end date of addition of short-acting bronchodilators can thus be retrieved from the patient application. The documented use of additional medication (Bedarfsmedikament) will be considered as a mild exacerbation with the following rules for start and end days:
  - A mild exacerbation must start with at least 2 consecutive days of additional medication reported, the first day of consecutive medication will determine the start of the exacerbation.
  - If there are gaps in the additional medication reporting, a maximum of 2 days is allowed to be considered only one exacerbation. A minimum of 70% of the days must have additional medication reported. The end date of the exacerbation is the last day where both these rules are fulfilled.
- Any exacerbations that happen within 5 days will be considered as overlapping, as well as exacerbations that have an intersection in their start and end dates. Overlapping exacerbations will be considered as only one and classified as the graver one. (4)
  - If all overlapping exacerbations have the same type, the start date is the start date of the first exacerbation, and the end date of the last one.

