Frequency of additional medication	Self-reported activities	Self-reported use of additional medication	Count of the number of times the use of additional medication (Bedarfsmedikament) as a log activity is reported per day.

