### 3.4.5 Analysis of outcomes

#### 3.4.5.1 Primary Objective 1

Descriptive statistics will be reported in terms of mean (SD) or median (IQR) for continuous variables, as well as counts and frequency (%) for categorical variables of sensor collected data described in section 2.1.4, comprised of

- physical activity,
- heart rate,
- resting heart rate,
- heart rate variability (10 variables),
- temperature,
- respiration rate,
- ratio of in- vs. expiration time
- cough frequency,
- sleep pattern (hours of sleep),
- frequency of additional medication

measured for each patient

1. at baseline (Day 0),
2. in the period Day 8 to Day 14 (intra-individual period average),
3. from 14 days prior to an exacerbation onset, in a 7-day sliding time window, in a 3-days sliding time window, and a 1-day sliding time window,
4. at the onset of an exacerbation (first day of exacerbation period),
5. from the end of an exacerbation to 14 days after, in a 7-day sliding time window, in a 3-days sliding time window, and a 1-day sliding time window,
6. 14, 21, and 28 days after an exacerbation.

The analysis will be repeated for different exacerbation severities:

1. Exacerbations of any (moderate or severe) severity are counted
2. Only severe exacerbations are counted
3. Only moderate exacerbations are counted
4. Only mild exacerbations are counted

Results will be reported in one table per parameter, with descriptive statistics indexing rows and measurement times indexing columns.

For each continuous parameter, mean values will be plotted across all daily measurement time points during the 3-month observation period, together with 95% CIs based on the normal approximation (t-statistic).

### 3.4.5.2 Primary Objective 2

To predict moderate or severe COPD exacerbations by building a statistical model employing sensor-derived data and demographic and medical covariates.

To generate several features needed as input to the model a number of algorithms (e.g., self-learning algorithms) for obtaining derived parameters such as cough frequency, physical activities and sleep pattern will be developed first using the label dataset obtained via the app (see Section 3.4.3).

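### The self-reported reliever count is listed as sensor data and tabulated around mild events that the same log defines; no readable objective 2 analysis gives performance without self-reported labels

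*SAP*

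**What the plan says.** **Objective 1.** SAP 3.4.5.1 announces descriptive statistics "of sensor collected data described in section 2.1.4, comprised of" a list whose last item is "frequency of additional medication". SAP 3.4.3 defines that item as "Count of the number of times the use of additional medication (Bedarfsmedikament) as a log activity is reported per day", with self-reported activities as its only source. The section referred to, SAP 2.1.4, is headed "Sensor measurements by Vivalink wearable device and ePRO diary", so it pools patch and diary variables. The objective 1 tables, one per parameter, are repeated by severity, including a version that counts mild exacerbations only.

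**Mild exacerbations.** SAP 2.3.1 builds them from the same log. At least 2 consecutive days must carry a report, and "the first day of consecutive medication will determine the start of the exacerbation". The end date comes from a rule on gaps (at most 2 days) and density (at least 70% of days reported).

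**Objective 2.** Protocol 8.1 words it as "To predict moderate or severe COPD exacerbations by building a statistical model employing sensor-derived data and demographic and medical covariates". The protocol mapping (14.1.2) lists, under a heading separate from sensor data, self-reported activities that include "spray use, non-scheduled spray use", coughing and sputum. SAP 3.4.2 adds: "All available features will be considered in the predictive modelling". SAP 3.4.5.2 plans several algorithms, feature selection, performance metrics, and explanatory methods on the selected model.

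**The concern.** Two different problems share one variable.

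First, a reader of the objective 1 tables will take every listed parameter as a patch measurement. In the mild version, the reliever table will show a sharp change at onset that looks like a physiological signal but follows from how onset is defined.

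Second, the study is meant to support a future monitoring solution built on sensor data (Protocol 4 and 7). If the selected objective 2 model uses reliever, cough or sputum labels, its sensitivity and AUC describe the patch and the participant's own reporting together. The documents themselves give the log a route into the prediction window. Under SAP 2.3.1, a mild episode that overlaps a moderate or severe one, or falls within 5 days of it, is merged, and onset is set at the first moderate or severe start. Where the mild episode came first, its logged days sit just before the onset to be predicted. The documents do not say how often this will happen, so the size of the effect on objective 2 is unknown.

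**Working it through.** **Plan figures.** These are not in dispute. Expected events are 60 × 0.5 = 30. The Poisson probability of at least 18 events with mean 30 is 0.993, and 60/0.9 rounds up to 67. The need for 18 events is reproduced with a one-sided 95% exact limit (at least 13 of 18 correct; probability 0.958 at a true value of 0.85). The documents do not state the sidedness.

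**Onset rule (SAP 2.3.1).** Let L(d) = 1 if additional medication is logged on day d.

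- Onset s is the first day of a run of at least 2 logged days, so L(s) = 1 and the count is at least 1.
- If L(s − 1) were 1, then s − 1 and s would be consecutive logged days and onset would be s − 1. So L(s − 1) = 0.

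Both hold for every mild episode, whatever the disease process. Two limits apply. An episode starting on the first study day has no observed day before. Also, L = 0 means that no report was made, which may reflect a missed entry and not an absence of use.

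**Simulation.** The SAP start, gap, 70% and 5-day merging rules were applied to reliever days drawn at random over 90 days, with 4,000 simulated participants per row. The daily logging probability is an assumption, because the documents give none. Cells show the share of days with a report.

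| Assumed daily probability | Onset day | Day before | 14 days before | During episode |
|---|---|---|---|---|
| 0.05 | 100% | 0% | 4.5% | 98.6% |
| 0.10 | 100% | 0% | 8.8% | 96.8% |
| 0.20 | 100% | 0% | 16.7% | 92.1% |
| 0.30 | 100% | 0% | 24.1% | 86.8% |

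Pure noise gives a complete step at onset. The 14-day average stays nearer the background rate, so the rule does not dictate the earlier days in the same way. Nor does it fix how many uses are logged on a positive day.

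**Objective 2, texts side by side.**

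- Objective (Protocol 8.1): sensor-derived data plus demographic and medical covariates.
- Permitted inputs (Protocol 14.1.2, SAP 3.4.2): these plus self-reported labels.
- Outcome (Protocol 9.1.2.1, SAP 2.3.1): moderate or severe events, recorded by the site in the eCRF and identified by antibiotics or oral corticosteroids, an emergency visit or hospitalization. Short-acting bronchodilators appear in the moderate definition, but the app log does not decide whether an event is moderate or severe.
- Outputs (SAP 3.4.5.2): performance of the evaluated models, and PDP, ALE, LIME or Shapley-type explanations of the selected one.
- Sensitivity analyses (SAP 3.4.4, 3.4.6): imputation and missingness only.

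Nothing readable here gives performance with the labels removed.

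**Precision of the proposed comparison.** At a sensitivity of 0.85 the standard error is √(0.85 × 0.15/n). For n = 18 it is 0.084 (about ±0.17 at 95%); for n = 30 it is 0.065 (about ±0.13). These are for one model. The error of a paired difference depends on how far the models agree, which the documents cannot tell us.

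**The case against.** The strongest reply has four parts.

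1. **The mislabel is local.** It occurs only in the objective 1 list. The protocol mapping keeps self-reports apart from sensor data, and the sensor group for objective 3 (SAP 3.4.5.3) omits the reliever count. This stands.
2. **Self-reports are prespecified inputs for objective 2.** Whether the main model should exclude them is partly a design preference. This stands too, so the fix adds models beside the planned one and does not replace it.
3. **Attribution is already planned.** The log is stored as its own variable, and feature-level explanations will be produced. A reader might infer that the sensor contribution cannot be separated, or that only overall performance will be reported; the documents support neither. What remains is that explanations of one model that used the labels do not give sensitivity, specificity or AUC for a model that did not.
4. **Parts of the documents are not visible.** SAP numbering passes from 3.4.5.5 to 3.4.5.10 across redacted blocks, and the table plan appears only as a heading. No one can say that such an analysis is nowhere planned. SAP 3.4.5.2, where one would expect it, is readable and does not contain it.

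The study also calls itself exploratory and treats mild events as a side question. That lowers the stakes without removing the defect in the table.

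**Conclusion.** The point holds in a limited form. In SAP 3.4.5.1 one self-reported variable is wrongly listed as sensor data, and the onset step in its mild-only table is definitional: a report on 100% of onset days and on 0% of observed preceding days. This rests only on the start rule in SAP 2.3.1. It does not make the whole table empty.

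For objective 2 a reader might infer circularity, or that the log will carry the model. The documents support neither. Moderate and severe events are not defined by the log, and neither document states how often reliever use rises before them. What is established is an attribution gap: the readable plan reports no performance without self-reported labels, while the objective is worded in terms of sensors and covariates. Treating non-scheduled spray use as the label behind the reliever count is an assumption, but the gap remains without it because coughing and sputum labels are admitted as well. The sample size is unaffected.

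**What to change.** 1. **SAP 3.4.5.1.** Move the reliever count from the sensor list to a group headed as self-reported. Drop its mild-exacerbation table, or footnote that the change at onset follows from the definition.
2. **SAP 3.4.5.2.** Beside the all-features model, and on the same cross-validation folds, report the selected algorithm with:
   - (a) demographic and medical covariates only;
   - (b) covariates plus patch-derived features, with no app labels as direct predictors;
   - (c) covariates plus self-reported labels.

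   Give the differences (b) − (a) and all-features − (c) with confidence intervals, labelled descriptive.
3. **Limits of (b).** App labels may still train the cough, activity and sleep algorithms. State that sleep pattern continues to rest on self-reported bedtimes (SAP 3.4.3), so (b) is not wholly passive.

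The cost is SAP wording and three extra feature sets for one algorithm, with no new data. Running them for all five named algorithm families would mean 3 × 5 = 15 fits, which is not needed. The downsides are that performance without labels may be lower, and that with about 18 to 30 events the differences may be too imprecise to settle what the patch adds.
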